4.5 SAFETY ANALYSES

The safety analysis population will consist of all randomized participants who received at least one dose of study drug, with participants grouped according to treatment and first dose received after randomization.

The main analyses will be done with a while on treatment strategy for two analyses sets: double-blind and overall satralizumab treatment period, which refers to the time in which participants are either randomized to satralizumab or switch to satralizumab at the beginning of the OLE period. The two analysis sets are defined as follows:

Analysis Set for the Double-Blind: All data up to the first dose in OLE, or up to 4 weeks after the last dose of the study drug (for participants who permanently discontinued the double-blind treatment), or last contact with the participant, or CCOD, whatever occurs first.

Analysis Set for the 'Overall Satralizumab Treatment': All data from the first dose of satralizumab (in the DB for the participants receiving satralizumab and in the **OLE for participants receiving placebo during the DB period**) until up to 4 weeks after the last dose of the satralizumab (for participants who permanently discontinued satralizumab), or last contact with the participant, or CCOD, whatever occurs first.

In addition, the data collected in the remaining period of the safety follow-up will be described separately and will use the analyses set for safety follow-up: all data later than 4 weeks after the last dose of study drug, for participants who permanently discontinued from the study drug.

Safety will be assessed through summaries of exposure to study treatment, AEs, changes in targeted laboratory test results, and changes in vital signs and electrocardiograms (ECGs).

Study treatment exposure (such as treatment duration, total dose received, and number of doses and dose modifications) will be summarized with descriptive statistics.

AE analyses will be performed on key subgroups including, but not limited to, age, race and region.

4.5.1 Extent of Exposure

Exposure to study drug information will be descriptively summarized by treatment as follows:

- Treatment duration (in days)
- Total number of administrations
- Total cumulative dose (mg)
- Frequencies of participants in each dose level
- Percentage of patients with a dose change due to weight changes.

Exposure to concomitant medications will be shown in a list overall and by treatment group showing the total number of uses of concomitant medications.

4.5.2 Adverse Events

All verbatim AE terms will be coded using the Medical Dictionary for Regulatory Activities version that is current at the time of the analysis (AE intensity will be graded according to the National Cancer Institute Common Terminology Criteria for Adverse Events, version 5.0 (NCI CTCAE, v5.0) grading scale or according to Table 11 in Section 5.3.3 of the

Study Protocol (mild/moderate/severe/life-threatening/death), if the event is not specifically listed in the NCI CTCAE. For each treatment group, the frequency of each AE preferred term will be defined as the number of participants experiencing at least one occurrence of the AE. Each table will present the overall number of events and percentage of participants experiencing at least one AE.

Additional analyses for the 'overall satralizumab treatment' analysis set, summary of AE per 100 participant years will be provided. In this analysis multiple events will be counted each time they occur.

Percentages will be based on the number of participants in the safety-evaluable analysis population. In summary tables, AEs will be sorted by body system (in decreasing order of overall incidence), then by preferred term (in decreasing order of overall incidence).

The following safety information will be summarized by treatment group for the double-blind treatment period:

- AEs, AEs by intensity, AEs related to study drug
- Deaths
- Serious adverse events (SAEs), SAEs related to study drug
- AEs leading to discontinuation of study treatment
- AEs leading to dose modifications (dose interruption)
- Protocol-specified adverse events of special interest
- Infections
- Injection reactions.

The following data handling rules will be applied for all AE summary tables:

- Events that are missing both at onset and at end dates will be considered to have started after the first dose of study drug and the duration will be set to missing.
- If the onset date is missing, and the end date is on or after the first dosing date or unresolved or missing, then the event will be considered to have started after the first dose of study drug.

4.5.3 Laboratory Data

Laboratory data will be summarized by treatment group using descriptive statistics of absolute values and change from baseline values. In addition, the frequency of participants with abnormal laboratory values will be summarized by treatment group, visit, and baseline status.

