# 5.1.1.4 Neutropenia

In the DB period of the Phase III studies in NMOSD patients, decreases in neutrophil counts (including Grade 3 and Grade 4) occurred following treatment with satralizumab. The majority of neutrophil decreases were transient or intermittent.

Participants with a low neutrophil count ( $< 2 \times 10^3/\mu L$ ) will be excluded from the study (see Section 4.1.2.4).

Recommended dose interruption or discontinuation for absolute neutrophil counts (ANC) decreases are shown in Table 9.

Table 9 Management of Neutropenia Low Neutrophil Count

ANC (/μL)	Action to Be Taken
>1,000	Maintain dose.
500–1,000	• If neutropenia persists, the study drug should be interrupted until ANC is above 1,000/ $\mu$ L (for restarting study drug administration please refer to Section 4.3.2.2).
	• If ANC was under 1,000/µL at the previous laboratory test, ANC must be checked before treatment with the study drug (e.g., ANC test at site).
< 500	Study drug should be discontinued.

ANC = absolute neutrophil count.

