# 5.1.1.5 Thrombocytopenia

In Phase III studies in NMOSD patients, decreases in platelet counts were observed in patients treated with satralizumab. The majority of the decreased platelets were transient and not below  $75 \times 10^9 / L$ .

Patients with Platelet count  $< 10 \times 10^4/\mu L$  at screening will be excluded from the study (see Section 4.1.2.4).

Recommended dose interruption on the basis of platelet counts are shown in Table 10.

Table 10 Management of Low Platelet Count

Platelet Count (/μL)	Action
>75,000	Maintain dose.
50,000–75,000	
 
If thrombocytopenia persists, the study drug should be interrupted until platelet count is above 75,000 cells/μL (for restarting study drug administration please refer to Section 4.3.2.2).
 

< 50,000	The study drug should be discontinued.

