# 5.3.5.5 Abnormal Laboratory Values

Not every laboratory abnormality qualifies as an adverse event. A laboratory test result must be reported as an adverse event if it meets any of the following criteria:

- Is accompanied by clinical symptoms
- Results in a change in study treatment (e.g., dosage modification, treatment interruption, or treatment discontinuation)
- Results in a medical intervention (e.g., potassium supplementation for hypokalemia) or a change in concomitant therapy
- Is clinically significant in the investigator's judgment

It is the investigator's responsibility to review all laboratory findings. Medical and scientific judgment should be exercised in deciding whether an isolated laboratory abnormality should be classified as an adverse event.

If a clinically significant laboratory abnormality is a sign of a disease or syndrome (e.g., alkaline phosphatase and bilirubin 5 × ULN associated with cholestasis), only the diagnosis (i.e., cholestasis) should be recorded on the Adverse Event eCRF.

If a clinically significant laboratory abnormality is not a sign of a disease or syndrome, the abnormality itself should be recorded on the Adverse Event eCRF, along with a descriptor indicating whether the test result is above or below the normal range (e.g., "elevated potassium," as opposed to "abnormal potassium"). If the laboratory abnormality can be characterized by a precise clinical term per standard definitions, the clinical term should be recorded as the adverse event. For example, an elevated serum potassium level of 7.0 mEq/L should be recorded as "hyperkalemia."

Observations of the same clinically significant laboratory abnormality from visit to visit should only be recorded once on the Adverse Event eCRF (see Section 5.3.5.4 for details on recording persistent adverse events).

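### SAP 4.5.3 counts laboratory abnormalities visit by visit and without grade, so it does not commit to the number per arm who ever reached a given neutrophil grade

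*SAP*

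**What the plan says.** SAP 4.5.3 (Laboratory Data) has two sentences. The first plans descriptive statistics of values and changes from baseline by arm. The second says that "the frequency of participants with abnormal laboratory values will be summarized by treatment group, visit, and baseline status". Neither mentions a CTCAE grade, an ANC limit, a count over the whole period or a worst value.

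Elsewhere, SAP 4.5.2 applies CTCAE grading to adverse events, and SAP 4.5.6 plans a worst post-baseline summary for the C-SSRS only.

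On neutrophils, Protocol 5.1.1.4 reports that in the double-blind NMOSD Phase III data "decreases in neutrophil counts (including Grade 3 and Grade 4) occurred following treatment with satralizumab", and adds: "The majority of neutrophil decreases were transient or intermittent". Table 9 of that section sets three bands:

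- Above 1,000/µL, the dose is maintained.
- At 500-1,000/µL, "If neutropenia persists, the study drug should be interrupted until ANC is above" 1,000/µL. If the previous result was under 1,000/µL, "ANC must be checked before treatment with the study drug".
- Below 500/µL, study drug should be discontinued.

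Protocol 5.3.5.5 states: "Not every laboratory abnormality qualifies as an adverse event". A result must be reported as an event if it comes with symptoms, changes study treatment, leads to an intervention or a change in concomitant therapy, or "Is clinically significant in the investigator's judgment".

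**The concern.** Neutropenia is a known effect of this drug. A safety reader will ask how many participants in each arm ever fell to a given grade. A by-visit count is a point prevalence, and it represents a transient or intermittent effect poorly. Without grades, a value just under the normal limit and a value under 1,000/µL fall in the same cell.

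The comparison between arms also matters. Protocol 3.4.8 lists myelosuppression among the risks of the background immunosuppressants that participants may be taking, so low counts can occur on placebo too.

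If the laboratory tables do not give the number ever affected, the reader must turn to the adverse event tables. There, inclusion can depend on an investigator's judgement rather than on the central laboratory result.

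**Working it through.** The plan states no figure on this point, so there is none to reproduce. The check is a bound followed by a comparison of sections.

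**1. What by-visit counts determine.** Let k_j be the number of participants in an arm with an abnormal value at visit j, and E the number with an abnormal value at any of those visits. Then max(k_j) ≤ E ≤ Σ k_j, capped at the arm size. With the same count k at two visits, E lies anywhere from k (the same people) to 2k (different people). The bounds coincide only if at most one visit count is non-zero. Persistent falls push E towards the lower bound and transient falls towards the upper. So E is not determined. Even if it were, it would be the number ever abnormal, not the number ever below a Table 9 limit.

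**2. Other planned summaries.** SAP 4.1 includes the range, which shows whether anyone in an arm was low, not how many. SAP Table 1 and Protocol 6.5 offer only changes in targeted laboratory results. SAP Section 5 says there are no supporting documents. None of these supplies the count.

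**3. The adverse event route, by ANC band (Table 9 set against Protocol 5.3.5.5).**

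- Below 500/µL: discontinuation is a treatment change, so reporting is required. SAP 4.5.2 then grades the event and counts each participant once per preferred term. Captured.
- 500-1,000/µL and persisting: interruption is a treatment change, so reporting is required. Captured.
- 500-1,000/µL and not persisting: dosing may continue. Reporting depends on symptoms, an intervention or the investigator's view. Not necessarily captured.
- Above 1,000/µL but low: no action is required. Not necessarily captured, and of less clinical interest.

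**4. What narrows the third band.** Protocol 4.5 allows dosing only when the clinical assessment and local laboratory results are acceptable, and a dose withheld for that reason is a treatment change. The recheck rule catches a value that is still low at the next dose. What remains is a value that recovered or was accepted for dosing, caused no symptoms, needed no intervention and was judged not clinically significant.

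**5. Overall satralizumab set.** SAP 4.5.2 lists its by-intensity summary for the double-blind period. What it adds for the overall set is a rate per 100 participant-years in which repeat events are counted each time, which is not a count of participants.

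**6. Values outside the schedule.** Protocol Appendix 1 also marks hematology at unscheduled and re-loading visits. SAP 4.5 takes all data into the safety sets, but the only rule for mapping values to visits (SAP 4.2.1.2) is for efficacy. The plan does not say in which visit such values are counted.

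**7. Other parameters.** For platelets, Protocol 5.1.1.5 says "The majority of the decreased platelets were transient and not below" 75 × 10^9/L. That equals 75,000/µL (75 × 10^9 ÷ 10^6), the top of the Table 10 interruption band. For ALT and AST, Table 8 withholds study drug above 3 × ULN, so such values should be reported as events. The need is greatest for ANC.

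**The case against.** The strongest case for the plan is that it delivers its stated endpoint. The safety endpoint is change from baseline in targeted laboratory results, SAP 4.5.3 provides that, and no objective in either document asks for a worst-grade table. Falls below 500/µL and persistent falls should reach the adverse event tables. Investigators must review every laboratory result, and neutrophils are not among the parameters named as blinded. The iDMC reviews unblinded safety data about every 3 months. Counting values below a fixed limit is simple arithmetic on central laboratory data, so the lack of pre-specification leaves little room for selective analysis.

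All of this stands, and it keeps the severity low. It does not supply the missing count, because no sentence in the SAP commits to one.

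A reader might infer more than the documents support:

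- **That severe neutropenia would go unreported.** It should not: discontinuation below 500/µL triggers event reporting.
- **That unscheduled values are discarded.** The safety sets take all data. The plan is only silent on where these values are placed.
- **That a worst-grade table is ruled out, or that the SAP contradicts the protocol.** Neither is so. The SAP simply does not specify the table.

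**Conclusion.** The point holds as a low-severity gap in descriptive safety reporting. SAP 4.5.3 as written does not yield the number per arm who ever reached a given neutrophil grade, and the adverse event tables make up for this only in part. The main practical loss is the transient, asymptomatic ANC of 500-1,000/µL.

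The size cannot be quantified. The documents give no incidence of such values in gMG, and none is assumed here. Efficacy analysis, estimands, alpha, data collection and iDMC review are unaffected.

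The conclusion assumes that the SAP is followed literally and that sites apply Table 9 and Protocol 5.3.5.5 as written. It also assumes that persistence is left to site judgement, since Table 9 gives no duration for it.

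**What to change.** Keep the by-visit tables and add to SAP 4.5.3:

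- For ANC, a shift table from baseline to worst post-baseline NCI CTCAE v5.0 grade, per participant and by arm, using all scheduled and unscheduled values.
- The same table for the double-blind set and for the overall satralizumab set defined in SAP 4.5. For participants who switch from placebo, use the active treatment baseline of Protocol 3.1.4. This has to be stated, because the default in SAP 4.1 is the last value before any study treatment.
- The number of participants ever below 1,000/µL in each set.

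Matching tables for platelets, ALT and AST are optional.

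The cost is a short addition to the SAP and two or three standard tables. One parameter in 2 analysis sets gives 2 shift tables, and the count below 1,000/µL is an added row or one further table. Each optional parameter would add 2 more. No new data are needed and no existing output is lost.

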4.5.4 Vital Signs

Vital signs assessments include systolic blood pressure, diastolic blood pressure, and pulse rate measured throughout the study. Vital sign measurements will be summarized by treatment group using descriptive statistics of absolute values and change from

baseline values. In addition, the frequency of participants with abnormal results will be summarized by treatment group, visit, and baseline status.

4.5.5 ECGs

ECG data will be summarized by treatment group for each assessment visit using descriptive statistics of absolute values and change from baseline values for the following parameters:

- Heart rate
- QRS duration
- RR interval
- PR interval
- QT interval

In addition, ECG overall interpretations will be summarized by treatment group and visit.

4.5.6 Columbia Suicide Severity Rating Scale (C-SSRS)

The Columbia Suicide Severity Scale (C-SSRS) is an assessment tool used to assess the lifetime suicidality of a participant (C-SSRS at baseline) as well as any new instances of suicidality (C-SSRS since last visit). The structured interview prompts recollection of suicidal ideation, including the intensity of the ideation, behavior, and attempts with actual or potential lethality.

- Suicidal ideation, suicidal behavior, and self-injurious behavior without suicidal intent
 will be summarized by treatment group at each assessment visit. In addition,
 change from baseline to worst post-baseline assessment in suicidality.
- Categories will be summarized by treatment group.

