# 4.5.7 Electrocardiograms

Single ECG recordings will be obtained at specified timepoints, as outlined in the schedule of activities (see Appendix 1 and Appendix 2), and may be obtained at unscheduled timepoints as indicated.

All ECG recordings must be performed using a standard high-quality, high-fidelity digital electrocardiograph machine equipped with computer-based interval measurements. Lead placement should be as consistent as possible. ECG recordings must be performed after the patient has been resting in a supine position for at least 10 minutes. All ECGs are to be obtained prior to other procedures scheduled at that same time (e.g., vital sign measurements, blood draws). Circumstances that may induce changes in heart rate, including environmental distractions (e.g., television, radio, conversation) should be avoided during the pre-ECG resting period and during ECG recording.

For safety monitoring purposes, the investigator must review, sign, and date all ECG tracings. Paper copies of ECG tracings will be kept as part of the patient's permanent study file at the site. The following should be recorded in the appropriate eCRF: heart rate, RR interval, QRS interval, PR duration, uncorrected QT interval, and QT interval corrected through use of Fridericia's formula (QTcF) on the basis of the machine readings of the individual ECG tracings. Any morphologic waveform changes or other ECG abnormalities must be documented on the eCRF. New or worsened abnormalities should be recorded as adverse events if clinically significant.

If at a particular timepoint the mean QTcF is > 500 ms and/or > 60 ms longer than the baseline value, another ECG must be recorded, ideally within the next 5 minutes, and ECG monitoring should continue until QTcF has stabilized on two successive ECGs. The Medical Monitor should be notified. SOC treatment may be instituted per the discretion of the investigator. If a PK sample is not scheduled for that timepoint, an unscheduled PK sample should be obtained. The investigator should also evaluate the patient for potential concurrent risk factors (e.g., electrolyte abnormalities, co-medications known to prolong the QT interval, severe bradycardia).

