1. INTRODUCTION

This Statistical Analysis Plan (SAP) details the planned analyses and considerations of statistical methodology for Study WN42636. Study WN42636 is a Phase III, randomized, placebo-controlled, double-blind, multicenter clinical study to evaluate the efficacy, safety, pharmacokinetic (PK), and biomarker effects of satralizumab in participants with generalized Myasthenia Gravis (gMG). For background information about the study, please refer to the Study Protocol WN42636. The analyses described in this SAP will supersede any analysis described in the Protocol for regulatory filings.

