		•	Time to disease worsening as measured by the time from baseline to:
			 Start of rescue therapy
			 MG-related exacerbation
•	QoL		Mean change from baseline to Week 24 in EuroQoL EQ-5D-5L Health Utility Index score ^b

 Table 1
 Objectives and Corresponding Endpoints

Safety Objective	Corresponding Endpoints
To evaluate the safety of satralizumab versus placebo	Incidence and severity of adverse events, with severity determined according to NCI CTCAE v5.0 grading
	Change from baseline in targeted vital signs, ECG results, targeted clinical laboratory test results, and suicidality
Pharmacodynamic Objective	Corresponding Endpoint
To confirm target engagement and pathway inhibition in response to satralizumab	Absolute values and change from baseline in serum levels of biomarkers IL-6 and sIL-6R
Pharmacokinetic Objective	Corresponding Endpoints
To investigate the PK of satralizumab by evaluating plasma exposure over	Serum concentrations of satralizumab (mean and SD of Ctrough) at specified timepoints b
24 weeks	 Estimates of primary PK parameters (e.g., CL/F and V/F) and secondary PK parameters (e.g., AUC) derived using population-PK modeling ^b

Table 2 Objectives and Corresponding Endpoints

Exploratory Pharmacokinetic Objective	Corresponding Endpoints
To evaluate potential relationships between drug exposure and the efficacy and safety of satralizumab	 Relationship between selected covariates and exposure to satralizumab b Relationship between serum concentration or PK parameters for satralizumab and efficacy endpoints, PD biomarkers, and safety endpoints b
Immunogenicity Objective	Corresponding Endpoint
To evaluate the immune response to satralizumab	 Prevalence of ADAs at baseline and incidence of ADAs during the study
Exploratory Immunogenicity Objective	Corresponding Endpoint
To evaluate potential effects of ADAs on efficacy, biomarker, safety, and PK endpoints	 Relationship between ADA status, biomarker, safety, or PK endpoints
Exploratory Biomarker Objective	Corresponding Endpoint
To identify and/or evaluate biomarkers that are predictive of response to satralizumab, can provide evidence of satralizumab activity, or can increase the knowledge and understanding of disease biology	Relationship between biomarkers in blood and efficacy endpoints ^b

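### The SAP's ECG summary lists QT interval but omits QTcF, the rate-corrected value that the protocol records and uses for its only ECG interval limits

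*SAP*

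**What the plan says.** Protocol 4.5.7 requires heart rate, RR, QRS and PR in the eCRF, together with "uncorrected QT interval, and QT interval corrected through use of Fridericia's formula (QTcF"), taken from the machine readings. QT and QTcF are thus two separate fields. The same section sets a follow-up rule that begins "If at a particular timepoint the mean QTcF is > 500 ms and/or > 60 ms longer than the baseline value". It leads to a repeat ECG, continued monitoring, notification of the Medical Monitor and, if none is scheduled, a PK sample. No other ECG interval has a numerical limit in the protocol.

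Change from baseline in ECG results is a named safety endpoint. SAP 1.1 words it as "Change from baseline in targeted vital signs, ECG results, targeted clinical laboratory test results, and suicidality", without the footnote that marks endpoints reported outside the SAP.

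For the analysis, SAP 4.5.5 says that "ECG data will be summarized by treatment group for each assessment visit using descriptive statistics of absolute values and change from baseline values" and names five parameters: heart rate, QRS duration, RR, PR and QT interval. The only further ECG output is this: "In addition, ECG overall interpretations will be summarized by treatment group and visit". Under SAP section 1, "The analyses described in this SAP will supersede any analysis described in the Protocol for regulatory filings", so the SAP list governs the submission tables.

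**The concern.** QT shortens as heart rate rises and lengthens as it falls. Correction exists so that a change in repolarisation can be read apart from a change in rate. The protocol follows that logic: it records the Fridericia-corrected value and sets its limits on it. The SAP then summarises every recorded rate and interval parameter except that one.

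Two things are lost. First, if heart rate shifts within an arm or differs between arms, mean change in raw QT carries the rate effect as well as any repolarisation effect, and no planned table separates them. Second, the protocol's own limits cannot be counted by arm. A participant's QTcF cannot be recovered from tables of group means for QT, RR and heart rate.

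**Working it through.** **Step 1. Set the two lists side by side.**

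| Parameter | Recorded in eCRF (protocol 4.5.7) | Protocol limit | Listed in SAP 4.5.5 |
|---|---|---|---|
| Heart rate | yes | none | yes |
| RR | yes | none | yes |
| QRS | yes | none | yes |
| PR | yes | none | yes |
| QT, uncorrected | yes | none | yes (as QT interval) |
| QTcF | yes | > 500 ms; > 60 ms above baseline | **no** |

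Five of six recorded parameters are listed. The missing one is the only one with limits. The SAP does not itself say that its QT interval is uncorrected. That is a reading, made because no correction is named and the protocol keeps the two fields apart.

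**Step 2. Look for QTcF elsewhere.** It is not in the SAP abbreviation list or any other SAP section. Protocol 6.5 says only that ECG changes will be summarised. SAP section 5 states that there are no additional supporting documents. SAP 4.5.3 and 4.5.4 give counts of abnormal laboratory and vital-sign results; SAP 4.5.5 gives none for ECG intervals, only the overall interpretation.

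**Step 3. Size of the heart-rate effect on one ECG.** The documents give no QT values and no expected heart-rate change, so the inputs are assumptions: QTcF constant at 410 ms and heart rate 60, 75 or 90 bpm.

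Fridericia: QTcF = QT / RR^(1/3), with RR = 60/HR in seconds. Hence QT = QTcF × (60/HR)^(1/3).

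- HR 60: QT = 410 × 1 = 410.0 ms.
- HR 75: QT = 410 × 0.8^(1/3) = 410 × 0.9283 = 380.6 ms, a change of −29.4 ms.
- HR 90: QT = 410 × 0.6667^(1/3) = 410 × 0.8736 = 358.2 ms, a change of −51.8 ms.

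Against the protocol's 60 ms limit these are 29.4/60 = 49% and 51.8/60 = 86%, with no change in QTcF at all.

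**Step 4. The reverse case, also with assumed values.** A QT of 440 ms at 90 bpm gives QTcF = 440 / 0.8736 = 503.7 ms. The ECG is above the 500 ms limit although the raw QT is 60 ms below that figure.

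**The case against.** Several objections carry weight.

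- **The table is not blind to heart rate.** Heart rate and RR are summarised by arm and visit, and the double-blind comparison is randomised against placebo. A rate shift common to both arms largely cancels, and a shift in one arm only would be visible. A reader might infer that the planned table cannot show any effect on repolarisation; that goes too far. What stands is that there is no direct rate-corrected summary. The overall satralizumab analysis set in SAP 4.5 also includes open-label data, which have no concurrent control.
- **The arithmetic describes one ECG, not an arm mean.** For distortion of that size in the between-arm comparison, mean heart rate in one arm would have to change by 15 to 30 bpm more than in the other. Nothing in the documents suggests this. A reader might also take 29 or 52 ms as equal to a clinically relevant signal. The only change limit in the documents is 60 ms, and both figures are below it.
- **No commitment was broken.** The protocol promises a summary of ECG changes, not specifically of QTcF, and its limits are follow-up rules for individual patients. A reader might infer a contradiction between protocol and SAP; there is none, and SAP Appendix 1 had no planned QTcF analysis to report as changed.
- **Other outputs cover part of the ground.** Clinically significant new or worsened ECG abnormalities are recorded as adverse events and tabulated by arm, overall interpretations are summarised, and the iDMC reviews unblinded safety data about every 3 months. None of these supplies QTcF values or counts.
- **No repolarisation risk is listed** in protocol 5.1 for satralizumab or its class. This lowers the priority, but it does not explain listing QT without QTcF.

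**Conclusion.** The omission is real and minor. Followed as written, the SAP summarises the ECG safety endpoint with a rate-dependent QT measure and leaves out the corrected value that the protocol records. The protocol's limits of 500 ms and 60 ms cannot be counted by arm from the planned tables. How far raw QT would mislead depends on heart-rate changes that the documents do not predict; the 29 ms and 52 ms figures only show the scale on a single ECG under assumed values. The conclusion rests on reading QT interval in SAP 4.5.5 as uncorrected. If QTcF was meant, the SAP still needs to say so. The output is descriptive, so the primary analysis and type I error are untouched.

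**What to change.** In SAP 4.5.5:

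1. Add QTcF to the parameter list, summarised as absolute value and change from baseline by arm and visit. Keep QT; this supplements it and does not replace it.
2. Add one categorical table by arm: participants with any post-baseline QTcF above 500 ms, and participants with any increase above 60 ms from baseline. These are the protocol's own limits, used here only for counting; patient follow-up under protocol 4.5.7 is unchanged.
3. State which reading enters the counts. Protocol 4.5.7 specifies single recordings but words its rule in terms of a mean QTcF, so the rule for repeat ECGs at a timepoint should be fixed before unblinding.

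The cost is one more parameter in an existing table and one small new table, both from data already in the eCRF. No new assessment is needed.
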